5.4.1 Durvalumab Dose Modification

Dose reductions for durvalumab are not permitted. For dose modification and toxicity management guidelines for durvalumab, refer to Appendix G.

5.4.2 *Olaparib dose levels*

Dose Level	Olaparib
Level 0	300 mg BID
Level -1	250 mg BID
Level -2	200 mg BID
Level -3	Discontinue

Subjects requiring more than two dose reductions will have to discontinue olaparib. 100 mg and 150 mg tablets will be supplied for olaparib.

5.4.3 *Toxicities that require discontinuation from study treatment*

Protocol therapy should be discontinued if a subject experiences:

- Any CTCAE Grade 4 toxicity with the exception of:
 - CTCAE Grade 4 neutropenia of 5 days or fewer duration
 - CTCAE Grade 4 nausea/vomiting or diarrhea that resolves to Grade 3 or less within 72 hours
 - CTCAE Grade 4 laboratory abnormalities that can be readily corrected with 72 hours and do not result in hospitalization.
- CTCAE Grade 3 thrombocytopenia with hemorrhage
- CTCAE Grade 3 febrile neutropenia
- Hy's Law (AST or ALT >3x ULN with concomitant serum bilirubin >2x ULN and no alternate etiology)
- Bone marrow findings consistent with myelodysplastic syndrome (MDS)/acute myeloid leukemia (AML)

5.5 **Concomitant Medications and Supportive Care**

Because of the potential for drug-drug interaction, the concurrent use of all other drugs, over-the-counter medications, and alternative therapies must be documented on the eCRF.

Subjects should not donate blood while participating in this study or for at least 90 days following the last infusion of durvalumab or olaparib.

Refer to Appendix D for more information on concomitant medications and supportive care guidance.

5.6 **Other Concomitant Treatment**

Any medications, with the exceptions noted in Appendix D, which are considered necessary for the subject's welfare, and which it is believed will not interfere with the study medication, may be given at the discretion of the Investigator, providing the medications, the doses, dates and reasons for administration are recorded in the EDC.

In addition, any diagnostic, therapeutic or surgical procedure performed during the study period must be recorded in the EDC.

All medications (prescriptions or over-the-counter medications) continued at the start of the trial (from the time of informed consent) or started during the study or until 30 days from the end of the last protocol treatment and different from the study medication must be documented.

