- blank lines for quantity of tablets to be taken
- date of dispensing
- Instructions stating that the olaparib tablets should be taken at approximately the same time each morning and evening

Storage Requirements

All study drugs should be kept in a secure place under appropriate storage conditions. The investigational product label on the bottle and the IB specifies the appropriate storage.

Subjects will continue treatment until disease progression, unacceptable toxicity or other reason for discontinuation of protocol treatment (Section 5.6).

Intake Calendar: Olaparib compliance will be recorded on an Intake Calendar/Pill Diary. Institutional staff will review and ascertain subject adherence with protocol treatment. If a dose is missed, subjects are to take the normal dose on the following day. If more than one daily dose is missed, the study doctor or study team must be informed.

Pharmacokinetics

Absorption

Following oral administration of olaparib via the capsule formulation, absorption is rapid with peak plasma concentrations typically achieved between 1 to 3 hours after dosing. On multiple dosing there is no marked accumulation (accumulation ratio of 1.4 – 1.5 for twice daily dosing), with steady state exposures achieved within 3 to 4 days.

Limited data suggest that the systemic exposure (AUC) of olaparib increases less than proportionally with dose over the dose range of 100 to 400 mg, but the PK data were variable across trials.

Co-administration with a high fat meal slowed the rate (T_{max} delayed by 2 hours) of absorption, but did not significantly alter the extent of olaparib absorption (mean AUC increased by approximately 20%).

Distribution

Olaparib had a mean (\pm standard deviation) apparent volume of distribution at steady state of 167 ± 196 L after a single 400 mg dose of olaparib. The *in vitro* protein binding of olaparib at plasma concentrations achieved following dosing at 400 mg twice daily is approximately 82%.

Metabolism

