In vitro, CYP3A4 was shown to be the enzyme primarily responsible for the metabolism of olaparib. Following oral dosing of ^{14}C -olaparib to female patients, unchanged olaparib accounted for the majority of the circulating radioactivity in plasma (70%). It was extensively metabolized with unchanged drug accounting for 15% and 6% of radioactivity in urine and feces, respectively. The majority of the metabolism is attributable to oxidation reactions with a number of the components produced undergoing subsequent glucuronide or sulfate conjugation.

Excretion

A mean (\pm standard deviation) terminal plasma half-life of 11.9 ± 4.8 hours and apparent plasma clearance of 8.6 ± 7.1 L/h were observed after a single 400 mg dose of olaparib.

Following a single dose of ^{14}C -olaparib, 86% of the dosed radioactivity was recovered within a 7-day collection period, 44% via the urine and 42% via the feces. The majority of the material was excreted as metabolites.

Based on preliminary data from a dedicated renal impairment trial, the mean AUC and C_{\max} of olaparib increased by 1.5 and 1.2-fold, respectively, when olaparib was dosed in patients with mild renal impairment ($\text{CLcr} = 50-80$ mL/min; $N=14$) compared to those with normal renal function ($\text{CLcr} > 80$ mL/min; $N=8$). There are no data in patients with $\text{CLcr} < 50$ mL/min or in patients on dialysis.

Drug Interactions

In vitro, olaparib was an inhibitor of CYP3A4 and an inducer of CYP2B6 at higher concentrations than are clinically achieved. Olaparib produced little/no inhibition of other CYP isozymes. *In vitro* studies have shown that olaparib is a substrate of CYP3A4.

Based on the data from a drug-interaction trial ($N=57$), the AUC and C_{\max} of olaparib increased by 2.7- and 1.4-fold, respectively, when olaparib was administered in combination with itraconazole, a strong CYP3A inhibitor. Simulations using physiologically-based pharmacokinetic (PBPK) models suggested that a moderate CYP3A inhibitor (fluconazole) may increase the AUC and C_{\max} of olaparib by 2- and 1.1-fold, respectively.

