APPENDIX D: MEDICATIONS WITH THE POTENTIAL FOR DRUG-DRUG INTERACTIONS

Olaparib is an investigational drug for which no data on in vivo interactions are currently available. Based on in vitro data and clinical exposure data, olaparib is considered unlikely to cause clinically significant drug interactions through inhibition or induction of cytochrome P450 enzyme activity. In vitro data have, however, also shown that the principal enzyme responsible for the formation of the 3 main metabolites of olaparib is CYP3A4 and consequently, to ensure subject safety, the following potent inhibitors of CYP3A4 must not be used during this study for any subject receiving olaparib.

While this is not an exhaustive list, it covers the known potent inhibitors, which have most often previously been reported to be associated with clinically significant drug interactions.

Prohibited Concomitant Medications while subjects are taking Olaparib:

Agent	Agent
ketoconazole	rifapentine
itraconazole	rifabutin
ritonavir	carbamazepine
indinavir	phenobarbitone
saquinavir	nevirapine
telithromycin	modafinil
clarithromycin	St John's Wort (Hypericum perforatum)
nelfinavir	
phenytoin	
rifampicin	

After enrollment if the use of any potent inducers or inhibitors of CYP3A4 are considered necessary for the subject's safety and welfare, the Sponsor Principal Investigator must contact the AstraZeneca Study Physician. A decision to allow the subject to continue in the study will be made on a case-by-case basis.

If there is no suitable alternative concomitant medication then the dose of olaparib should be reduced for the period of concomitant administration. The dose reduction of olaparib should be recorded in the CRF with the reason documented as concomitant CYP3A inhibitor use.

- Strong CYP3A inhibitors – reduce the dose of olaparib to 100mg BID for the duration of concomitant therapy with the strong inhibitor and for 5 half-lives afterwards.
- Moderate CYP3A inhibitors - reduce the dose of olaparib to 150mg BID for the duration of concomitant therapy with the moderate inhibitor and for 3 half-lives afterwards.
- After the washout of the inhibitor is complete, the olaparib dose can be re-escalated.

Strong or Moderate CYP3A inducers

Strong (e.g., phenobarbital, phenytoin, rifampicin, rifabutin, rifapentine, carbamazepine, nevirapine, enzalutamide and St John's Wort) and moderate CYP3A inducers (e.g. bosentan, efavirenz, modafinil) of CYP3A should not be taken with olaparib.

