Non-hematologic toxicities including nausea, vomiting, and diarrhea	Grade 1 and Grade 2 If subjects develop intolerable Grade 1 or Grade 2 toxicities (per subject) then they can undergo a dose reduction. For Grade 4 toxicities despite optimal medical therapy, hold olaparib until equal or under Grade 1. Resume at one dose level reduction. Events of nausea and vomiting are known to be associated with olaparib treatment. In study, they are generally mild to moderate (CTCAE Grade 1 or Grade 2) severity, intermittent and manageable on continued treatment. The first onset generally occurs in the first month of treatment with the incidence of nausea and vomiting not showing an increase over the treatment cycles.

		No routine prophylactic anti-emetic treatment is required at the start of study treatment; however, subjects should receive appropriate anti-emetic treatment at the first onset of nausea or vomiting and as required thereafter, in accordance with local treatment practice guidelines
General non-hematologic toxicities excluding nausea, vomiting, and diarrhea	Grade 3 or higher toxicities	Delay until recovery to Grade 1 or lower and reduce one dose level to 250mg BID). A maximum of 2 dose reductions can be made for repeat toxicity.
Anemia	CTCAE Grade 1 or Grade 2 (Hemoglobin (Hb) > 8 g/dl)	Investigate and manage as deemed appropriate by the investigator with or without interruption of study drug or change in dose, taking into account previous history of anemia. Common treatable causes of anemia (e.g., iron, vitamin B12 or folate deficiencies and hypothyroidism) should be excluded. In some cases, management of anemia may require blood transfusions.
	CTCAE Grade 3 (Hb < 8g/dl) or worse	
Study treatment should be interrupted for up to maximum of 4 weeks to allow for bone marrow recovery and the subject should be managed appropriately. Study treatment can be restarted at the reduced dose if Hb has recovered to > 10 g/dl. Any subsequently required anemia related interruptions, considered likely to be dose related, or coexistent with newly developed neutropenia, and or thrombocytopenia, will require a further study treatment dose reduction to 200 mg BID.
 
If a subject has been treated for anemia with multiple blood transfusions without study treatment interruptions and becomes blood transfusion dependant as judged by investigator, study treatment should be permanently discontinued.

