Neutropenia and leukopenia	CTC Grade 3 or worse neutropenia occurs	
Manage as deemed appropriate by the investigator with close follow up and interruption of study drug. Primary prophylaxis with Granulocyte colony-stimulating factor (G-CSF) is not recommended, however, if a subject develops febrile neutropenia, study treatment should be stopped and appropriate management including G-CSF should be given according to local hospital guidelines. Please note that G-CSF should not be used within at least 24 h of the last dose of study treatment.
 
Study treatment can be restarted at the same dose if an AE of neutropenia or leukopenia have been recovered up to CTC AE Grade less than or equal to Grade 1 (ANC > 1.5 x 10⁹/L). Growth factor support should be stopped at least 24h before restarting study drug (7 days for pegylated G-CSF).
 
Any subsequent interruptions will require study treatment dose reductions to 250 mg BID as a first step and to 200 mg

		BID as a second step for a 300 mg monotherapy starting dose
Thrombocytopenia	CTCAE Grade 3 or worse	
Study treatment should be interrupted for a maximum of 4 weeks. In some cases, management of thrombocytopenia may require platelet transfusions. Platelet transfusions should be done according to local hospital guidelines.
 
Any subsequent interruptions will require study treatment dose reductions to 250 mg BID as a first step and to 200 mg BID as a second step for a 300 mg monotherapy starting dose

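### Minor dosing-safety gap: Appendix D's flat 150 mg BID olaparib dose with a moderate CYP3A inhibitor undoes an earlier reduction to 250 or 200 mg BID, and Appendix H's daily-dose floor disagrees with section 5.4.2

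*Combined protocol and SAP*

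**What the plan says.** **Dose with an inhibitor.** If no suitable alternative medicine exists, Appendix D lowers olaparib to 100 mg BID with a strong CYP3A inhibitor. For the other class it says: "Moderate CYP3A inhibitors - reduce the dose of olaparib to 150mg BID for the duration of concomitant therapy with the moderate inhibitor". Neither dose depends on the subject's current dose level. After washout the dose may be raised again, with no stated ceiling.

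**Interaction data (section 6.2).** In a drug-interaction trial (N=57), olaparib AUC and Cmax "increased by 2.7- and 1.4-fold, respectively, when olaparib was administered in combination with itraconazole, a strong CYP3A inhibitor". For moderate inhibitors there is only a simulation with fluconazole, which suggests a rise in the AUC and Cmax "of olaparib by 2- and 1.1-fold, respectively". On dose dependence, limited data suggest that AUC "increases less than proportionally with dose over the dose range of 100 to 400 mg, but the PK data were variable across trials".

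**How subjects come to lower doses.** Section 5.4.2 has levels of 300, 250 and 200 mg BID, then discontinuation: "Subjects requiring more than two dose reductions will have to discontinue olaparib". In Appendix H, later dose-related anemia interruptions "will require a further study treatment dose reduction to 200 mg BID", and later interruptions for neutropenia or thrombocytopenia require "dose reductions to 250 mg BID as a first step and to 200 mg BID as a second step". Appendix H also recommends 200 mg BID for moderate renal impairment, with investigator discretion.

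**Floor.** The toxicity-management text of Appendix H ends olaparib if a reduction below 200 mg daily is needed.

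**The concern.** The two inhibitor doses look derived from the 300 mg BID starting dose, yet they are written for everyone. A subject already at 200 mg BID because of anemia or a fall in creatinine clearance, who then needs a moderate inhibitor such as fluconazole or diltiazem, would go to 150 mg BID. The tablet dose falls but the AUC rises, which defeats the purpose of the earlier reduction.

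The gap matters most for moderate inhibitors. Appendix D's mandatory contact with the company's study physician covers only potent agents. Its prohibited list names none of the moderate inhibitors given as examples in section 3.2.7. Its instruction to monitor subjects on an inhibitor concerns changes in efficacy, not toxicity.

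The floor is a separate inconsistency: two sections give stopping doses that differ by a factor of two. The same amendment should settle both, because correcting the floor without mentioning interaction doses would place Appendix D's own doses below it.

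**Working it through.** **Inputs.** Dose levels 300, 250 and 200 mg BID and tablets of 100 and 150 mg (5.4.2). Inhibitor doses 150 mg BID (moderate) and 100 mg BID (strong) (Appendix D). AUC folds 2 (moderate) and 2.7 (strong); Cmax folds 1.1 and 1.4 (6.2).

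**Where the plan's doses come from.** Matching dose = current dose / AUC fold. From 300 mg BID: 300/2 = 150 mg, exactly the moderate dose; 300/2.7 = 111 mg, for which 100 mg is the nearest tablet. The documents do not state this derivation, but the figures fit it.

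**AUC relative to the subject's own current dose,** if AUC is proportional to dose: ratio = fold × Appendix D dose / current dose. Numerators: moderate 2 × 150 = 300; strong 2.7 × 100 = 270.

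| Current dose | Moderate, 150 mg BID | Strong, 100 mg BID |
|---|---|---|
| 300 mg BID | 300/300 = 1.00 | 270/300 = 0.90 |
| 250 mg BID | 300/250 = 1.20 | 270/250 = 1.08 |
| 200 mg BID | 300/200 = 1.50 | 270/200 = 1.35 |

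Relative to 300 mg BID without an inhibitor, the AUC is 1.00 (moderate) or 0.90 (strong) at every level.

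**Cmax relative to current dose.** Moderate: 1.1 × 150 = 165, so 165/250 = 0.66 and 165/200 = 0.83. Strong: 1.4 × 100 = 140, so 140/250 = 0.56 and 140/200 = 0.70. Peak levels are not raised.

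**How wrong could the fold be?** Break-even fold = current dose / Appendix D dose. Moderate: 250/150 = 1.67 and 200/150 = 1.33, against a simulated 2. Strong at 200 mg BID: 200/100 = 2.0, against an observed 2.7.

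**Less-than-proportional AUC.** Section 6.2 gives no exponent. As an assumption, take ratio = fold × (Appendix D dose / current dose)^b with b from 0.9 to 0.7. From 200 mg BID the ratios become 1.54 to 1.64 (moderate) and 1.45 to 1.66 (strong). From 250 mg BID they become 1.26 to 1.40 and 1.18 to 1.42. Relative to the 300 mg BID starting dose they become 1.07 to 1.23 and 1.01 to 1.25. The proportional figures are therefore at the low end.

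**The fix, checked the same way.** Moderate inhibitor with 100 mg BID: 2 × 100 = 200, so 200/250 = 0.80 and 200/200 = 1.00. With b from 0.9 to 0.7: 2 × (100/250)^b = 0.88 to 1.05 and 2 × (100/200)^b = 1.07 to 1.23. For a strong inhibitor at 200 mg BID the matching dose is 200/2.7 = 74 mg BID, below the smallest tablet.

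**Floor.** 200 mg BID = 400 mg per day; 200 mg per day = 100 mg BID. Appendix D's doses total 200 mg per day (strong) and 300 mg per day (moderate). Neither is below the printed floor, but both are below 400 mg per day.

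**The case against.** **No stated aim is breached.** The documents never say that the inhibitor doses should preserve a subject's current exposure. A flat dose that keeps AUC near the planned starting level is a coherent rule. That stands as a reason to call this an unaddressed contingency. It does not explain why a subject who could not tolerate starting-dose exposure should be returned to it.

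**Controls exist.** Section 3.2.7 excludes strong and moderate inhibitors at entry. Section 5.6 admits other medicines only if they are ones "which it is believed will not interfere with the study medication", and 5.1.4 is similar. Appendix D applies only when no alternative exists. Adverse events, blood counts and chemistry are checked every cycle, and Appendix H lets the investigator interrupt or reduce. With 32 subjects, few are likely to need both a reduction and an unavoidable inhibitor; the documents give no count. These controls limit the risk, but none sets the dose. From Cycle 3 the laboratory checks are monthly, so a short anti-infective course could fall between them.

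**The moderate fold is soft.** It is a simulation of one drug. True, but at 200 mg BID it would have to be 1.33 or less for the rise to vanish.

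**The floor has little effect.** Both 5.4.2 and Appendix H end olaparib after two reductions, so the stricter rule usually governs. This largely stands, with one exception: a renal reduction goes from 300 to 200 mg BID in one step and leaves one counted reduction unused. The printed floor could also be read as deliberate, since it equals the strong-inhibitor dose; its place among the toxicity rules makes a slip more likely.

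**Conclusion.** The point holds as a minor dosing-safety gap. With a moderate inhibitor, the written rule gives about 1.20 times the subject's own AUC at 250 mg BID and 1.50 times at 200 mg BID. With a strong inhibitor, the excess worth correcting is at 200 mg BID (about 1.35 times), and individual review already applies there. These figures assume dose-proportional AUC and the folds in section 6.2; they rise if AUC is less than proportional.

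Three stronger readings might be inferred and are not supported:

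- **That both flat doses fit only subjects at 300 mg BID.** This is so for moderate inhibitors. For strong ones, 250 mg BID (1.08) is at least as close a match as 300 mg BID (0.90).
- **That subjects are taken well above planned exposure.** On proportional AUC, exposure returns to 1.00 or 0.90 of the starting dose, and Cmax is below that of the current dose. Less-than-proportional AUC could put it somewhat higher. In renal impairment the comparison is uncertain: section 6.2 reports 1.5-fold AUC in mild impairment and has no data below 50 mL/min.
- **That the trial's result is at risk.** Sample size and the primary analysis are unaffected.

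The floor conflict, 200 against 400 mg per day, is real but seldom decisive.

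**What to change.** 1. **Appendix D.** Limit 150 mg BID with a moderate inhibitor to subjects at 300 mg BID, and use 100 mg BID (one supplied tablet per dose) for those at 250 or 200 mg BID. With a strong inhibitor, keep 100 mg BID at 300 and 250 mg BID. At 200 mg BID, hold olaparib during the inhibitor and washout, or set the dose in the existing case-by-case contact.
2. **Appendix D, with a cross-reference in 5.4.2.** State that interaction reductions are temporary, do not count toward the two-reduction cap or the floor, and are reversed only to the dose held before the inhibitor.
3. **Appendix H.** Make the floor a dose reduction for toxicity below 200 mg BID. Together with item 2, this keeps Appendix D's doses from triggering discontinuation.

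The cost is one wording amendment, with no added subjects or procedures. A few subjects at 250 mg BID would have slightly lower exposure with a moderate inhibitor (0.80 times on proportional AUC). A hold for a strong inhibitor that runs past 8 weeks would end olaparib under Appendix H; the case-by-case contact is the way around that. A lighter minimum is to extend that contact to any already-reduced subject who needs a moderate inhibitor, but this would leave the dose unwritten.

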3.2 Exclusion Criteria

- 3.2.1 No other malignancy from which the subject has been disease-free for less than 3 years, with the exception of adequately treated and cured non-invasive malignancies such as basal or squamous cell skin cancer or superficial bladder cancer.
- 3.2.2 Less than one month prior to treatment start from last prior regimen or radiation exposure. Prior radiotherapy to the prostate (adjuvant or salvage radiotherapy) is allowed.
- 3.2.3 No prior investigational use with an anti-PD(1) including durvalumab or anti-CTLA4 antibody.
- 3.2.4 No prior treatment with a PARP inhibitor, including olaparib.
- 3.2.5 No concomitant or prior therapy with any of the following: IL-2, interferon, or other non-study immunotherapy regimens; immunosuppressive agents; or chronic use of systemic corticosteroids within 6 weeks of treatment start. Exceptions include: intranasal, inhaled, topical steroids, or local steroid injections (e.g., intra articular injection); Systemic corticosteroids at physiologic doses not to exceed 10 mg/day of prednisone or its equivalent; Steroids as premedication for hypersensitivity reactions (e.g., CT scan premedication)
- 3.2.6 No receipt of live attenuated vaccine within 30 days prior to treatment start *Note: enrolled subjects should not receive live vaccine while receiving IP and up to 30 days after the last dose of study therapy*
- 3.2.7 Concomitant use of known strong CYP3A inhibitors (e.g., itraconazole, telithromycin, clarithromycin, protease inhibitors boosted with ritonavir or cobicistat, indinavir, saquinavir, nelfinavir, boceprevir, telaprevir) or moderate CYP3A inhibitors (e.g. ciprofloxacin, erythromycin, diltiazem, fluconazole, verapamil). The required washout period prior to treatment start is 2 weeks.
- 3.2.8 Concomitant use of known strong (e.g., phenobarbital, enzalutamide, phenytoin, rifampicin, rifabutin, rifapentine, carbamazepine, nevirapine and St John's Wort) or moderate CYP3A inducers (e.g., bosentan, efavirenz, modafinil). The required washout period prior to starting olaparib is 5 weeks for enzalutamide or phenobarbital and 3 weeks for other agents.

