5.1 Study Procedures

5.1.1 Informed consent and research/HIPAA authorization

Before initiating any protocol-specific screening activities, the scope of the study should be explained to each subject. Subjects should be consented in accordance with Section 11.3 Written Informed Consent, including completion of a research/HIPAA authorization.

5.1.2 *Inclusion/exclusion criteria*

During the screening period, subject eligibility will be determined according to the inclusion and exclusion criteria (Sections 3.1 Inclusion Criteria & 3.2 Exclusion Criteria).

5.1.3 *Demographics and medical history*

Demographics and medical history collected will include:

- Date of birth (or age if date of birth is not allowed to be collected by local regulations)
- Significant past and ongoing conditions
- Dates of the primary prostatectomy and pathologic state
- Dates of prior radiation therapy
- Dates of prior hormonal therapies

5.1.4 *Concomitant medications*

Concomitant medications are permitted while on study if the medication is not expected to interfere with the evaluation of safety or efficacy, and is not otherwise restricted or prohibited (see Appendix C for a listing of medications with the potential for drug interactions).

5.1.5 *Vital signs, height, and weight*

Vitals will include temperature, blood pressure, and pulse. Height and weight will also be collected as described in Appendix B.

5.1.6 *Performance Status*

Performance status will be assessed using ECOG or Karnofsky scales (Appendix A).

5.1.7 *Physical examination*

A complete physical examination will be performed at screening. A symptom-directed physical exam may be performed at subsequent visits.

5.1.8 *Histologic and radiologic (per PCWG3 and RECIST 1.1 criteria) confirmation of disease*

Pathologic confirmation of prostate cancer and no evidence of metastasis on conventional CT or Bone Scan.

5.1.9 *Laboratory tests*

Laboratory tests will be performed by local labs and will include:

- CBC with differential: white blood cells count (WBC), red blood cell count (RBC), hemoglobin (HGB), hematocrit (HCT), platelet count (UNVPLT), neutrophils (NEUTP), lymphocytes (LYMP), monocytes (MONP), eosinophils (EOSP), basophils (BASOP)). If absolute differentials not available please provide % differentials.

- PSA
- Serum testosterone (TEST)

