6.5 Treatment Delay

Subjects receiving durvalumab or olaparib who require therapy delay of more than 8 weeks due to toxicity will be removed from treatment but will be followed according to the schedule of assessments. If toxicity is attributed to a single agent, upon discussion with the Sponsor Principal Investigator, subjects may continue the other drug.

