If the use of any strong or moderate CYP3A inducers are considered necessary for the subject's safety and welfare this could diminish the clinical efficacy of olaparib.

If a subject requires use of a strong or moderate CYP3A inducer or inhibitor then they must be monitored carefully for any change in efficacy of olaparib.

P-gp inhibitors

It is possible that co-administration of P-gp inhibitors (e.g. amiodarone, azithromycin) may increase exposure to olaparib. Caution should therefore be observed.

Effect of olaparib on other drugs

Based on limited *in vitro* data, olaparib may increase the exposure to substrates of CYP3A4, P-gp, OATP1B1, OCT1, OCT2, OAT3, MATE1 and MATE2K.

Based on limited *in vitro* data, olaparib may reduce the exposure to substrates of CYP3A4, CYP1A2, 2B6, 2C9, 2C19 and P-gp.

The efficacy of hormonal contraceptives may be reduced if co administered with olaparib.

Caution should therefore be observed if substrates of these isoenzymes or transporter proteins are co-administered.

Examples of substrates include:

- CYP3A4 – hormonal contraceptive, simvastatin, cisapride, cyclosporine, ergot alkaloids, fentanyl, pimozide, sirolimus, tacrolimus and quetiapine
- CYP1A2 – duloxetine, melatonin
- CYP2B6 – bupropion, efavirenz
- CYP2C9 – warfarin
- CYP2C19 - lansoprazole, omeprazole, S-mephenytoin
- P-gp - simvastatin, pravastatin, digoxin, dabigatran, colchicine
- OATP1B1 - bosentan, glibenclamide, repaglinide, statins and valsartan
- OCT1, MATE1, MATE2K – metformin
- OCT2 - serum creatinine
- OAT3 -furosemide, methotrexate

Natural/Herbal Products

The use of any natural/herbal products or other traditional remedies should be discouraged, but use of these products, as well as use of all vitamins, nutritional supplements, and all other concomitant medications must be recorded in the case report form (CRF).

It is not recommended to consume grapefruit juice while on olaparib therapy.

Vaccines

Live virus and live bacterial vaccines, with the exception of shingles vaccine (live), should not be administered while the subject is receiving study medication until 30 days after the last dose of study therapy.

Anticoagulant Therapy

Subjects who are taking warfarin may participate in this trial; however, it is recommended that international normalized ratio (INR) be monitored carefully at least once per week for the first month, then monthly if the INR is stable. Subcutaneous heparin and low molecular weight heparin are permitted.

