Based on the severity of the imAE, durvalumab should be withheld and corticosteroids administered. Upon improvement to Grade \leq 1, corticosteroid should be tapered over \geq 28 days. More potent immunosuppressive agents such as TNF inhibitors (e.g., infliximab) should be considered for events not responding to systemic steroids. Alternative immunosuppressive agents not listed in this guideline may be considered at the discretion of the investigator based on clinical practice and relevant guidelines. With long-term steroid and other immunosuppressive use, consider need for *Pneumocystis jirovecii* pneumonia (PJP, formerly known as *Pneumocystis carinii* pneumonia) prophylaxis, gastrointestinal protection, and glucose monitoring.

Dose modifications of study drug/study regimen should be based on severity of treatment-emergent toxicities graded per NCI CTCAE version in the applicable study protocol.

AE Adverse event; CTC Common Toxicity Criteria; CTCAE Common Terminology Criteria for Adverse Events; imAE immune-mediated adverse event; NCI National Cancer Institute; NCCN National Comprehensive Cancer Network; ESMO European Society for Medical Oncology

Specific Immune-Mediated Reactions

Adverse Event	Severity Grade of the Event (NCI CTCAE version 5.0)	Dose Modifications	Toxicity Management
Pneumonitis/ Interstitial Lung Disease (ILD)	Any Grade (Refer to NCI CTCAE applicable version in study protocol for defining the CTC grade/severity)	General Guidance	
For Any Grade:
 
 Monitor subjects for signs and symptoms of pneumonitis or ILD (new onset or worsening shortness of breath or cough). Subjects should be evaluated with imaging and pulmonary function tests, including other diagnostic procedures as described below. Suspected pneumonitis should be confirmed with radiographic imaging and other infectious and disease-related aetiologies excluded and managed as described below. Initial work-up may include clinical evaluation, monitoring of oxygenation via pulse oximetry (resting and exertion), laboratory work-up, and high-resolution CT scan. Consider Pulmonary and Infectious Disease Consults.

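### Section 3.2.6 bars all live vaccines on treatment, Appendix D exempts live shingles vaccine over the same period, and nothing says which rule governs

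*Combined protocol and SAP*

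**What the plan says.** Four places in the combined protocol and SAP bear on the point.

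- **Section 3.2.6.** The entry rule is "No receipt of live attenuated vaccine within 30 days prior to treatment start". The attached note carries the rule into the study: "enrolled subjects should not receive live vaccine while receiving IP and up to 30 days after the last dose of study therapy". Neither names an exception.
- **Appendix D, Vaccines.** "Live virus and live bacterial vaccines, with the exception of shingles vaccine (live), should not be administered" during study medication, and until 30 days after the last dose.
- **Section 5.1.4.** A concomitant medication is allowed if it is not expected to interfere with the safety or efficacy evaluation and "is not otherwise restricted or prohibited (see Appendix C for a listing of medications with the potential for drug interactions").
- **Sections 5.5 and 5.6.** Section 5.5 says "Refer to Appendix D for more information on concomitant medications and supportive care guidance". Section 5.6 leaves to the investigator's discretion "Any medications, with the exceptions noted in Appendix D, which are considered necessary" for the subject's welfare and are believed not to interfere with study medication.

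The 3.2.6 note and the Appendix D paragraph do not refer to each other.

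**The concern.** One product over one period falls inside the first rule and outside the second. A clinician asked about a vaccine in mid-treatment is more likely to open the concomitant-medication appendix than the exclusion criteria, and would find live shingles vaccine expressly set apart there. At another site the same vaccination would be refused, or recorded as a departure from 3.2.6.

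The exemption is also unconditional: it does not mention blood counts, steroids or other immunosuppression. Yet Appendix G foresees systemic steroids for immune-mediated events and adds "More potent immunosuppressive agents such as TNF inhibitors (e.g., infliximab) should be considered for events not responding to systemic steroids", and Appendix H has rules for neutropenia and leukopenia. The protocol gives no reason for exempting this one live vaccine. At stake are consistent handling of a safety rule across sites and clear classification of deviations, not the efficacy result.

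**Working it through.** The plan has no figure to reproduce. The check compares the texts and then measures how long they disagree.

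**The two rules side by side**

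| | 3.2.6 note | Appendix D, Vaccines |
|---|---|---|
| Products | Live vaccine | Live virus and live bacterial vaccines |
| Exception | None | Live shingles vaccine |
| Start | While receiving study drug | While receiving study drug |
| End | 30 days after last dose | 30 days after last dose |
| Strength | Should not | Should not |

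The periods and the strength of wording match. The only difference is the exception.

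**Does another section settle it?**

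1. Section 5.1.4 excludes anything restricted elsewhere, so it favours 3.2.6. It does not rank conflicting texts. Its pointer for interacting drugs goes to Appendix C, which is the Hy's Law appendix, so it does not lead the reader to the vaccine paragraph.
2. Section 5.5 sends the reader to Appendix D and does not mention 3.2.6.
3. Section 5.6 treats Appendix D as the list of limits on the investigator's discretion. Live shingles vaccine is outside that list, so a site working from 5.6 could give it after judging it necessary and not likely to interfere with study medication.

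The result is two defensible readings and no clause to choose between them.

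**How long the texts disagree.** Inputs: a cycle is 28 days (Appendix B); up to 24 cycles (Sections 5 and 5.7); 30 days after the last dose (both rules). The period is cycles x 28 + 30, if olaparib is taken to the last day of the last cycle.

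- Full course: 24 x 28 = 672; 672 + 30 = **702 days**.
- Stopping after one cycle: 28 + 30 = 58 days.
- If durvalumab alone is being given at the end, the last dose is Day 1 of Cycle 24, which is day 23 x 28 + 1 = 645; 645 + 30 = 675 days, or 27 fewer.
- One tolerated 8-week delay: Section 6.5 says that subjects "who require therapy delay of more than 8 weeks due to toxicity will be removed from treatment", so 8 weeks is allowed. If the delayed cycles are made up, which the protocol does not state, 702 + 56 = 758 days.
- Re-induction with a full second course (Appendix B, footnote s), assuming all 24 cycles are repeated and the periods do not overlap: 2 x 702 = 1,404 days.

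These are durations of the disagreement, not frequencies. The documents do not say how many men would ask for the vaccine; the bounds are 0 and the 32 planned (Section 4.1.1).

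**The case against.** The strongest reply is that both texts can be obeyed at once. Appendix D does not recommend or require live shingles vaccine; it only leaves it out of one sentence. A site that withholds it breaches nothing, and 5.1.4 supports withholding. This stands as far as it goes and is a main reason the point is minor. It does not remove the conflict, because a site that follows 5.6 and Appendix D as written can give a vaccine that 3.2.6 says should not be given.

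A second reply is that the exemption is explicit and may be deliberate, with support in the Investigator's Brochures, which are not available here. The documents give no data for the exemption, but none specific to shingles vaccine for the ban either. This is fair. The mismatch is certain; the sponsor's intention is not. If the exemption was intended, 3.2.6 forbids what was meant to be allowed and the texts still need correcting.

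A third reply is that no passage links this vaccine to harm with steroids or infliximab, and that Appendix G describes itself as guidance. That also stands. The immunosuppression point shows only that the exemption carries no conditions; it does not establish a risk.

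Finally, the wrong appendix pointer in 5.1.4 is a separate slip. It does not create the conflict and adds little weight to it.

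**Conclusion.** The concern holds at minor severity. It is an inconsistency between two operative safety rules, with no order of precedence. For one uninterrupted course the rules disagree for 702 days, assuming olaparib runs to the end of Cycle 24; the figure is shorter with early stopping and longer with delays or re-induction. The number of men affected is unknown and may be 0. The size of any clinical risk cannot be judged from the documents. Nothing in the primary endpoint, the sample size or the toxicity stopping rule depends on it. Confidence is high that the texts conflict, and lower about which rule the sponsor intended.

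**What to change.** Delete the shingles exemption from the Vaccines paragraph of Appendix D, so that it matches the 3.2.6 note. This direction is preferred because 5.1.4 already leans to the stricter rule and the documents offer nothing in support of the exemption. If the sponsor did intend it, the alternative is to write it into the 3.2.6 note with conditions on blood counts and immunosuppression, and to repeat it identically in Appendix D.

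The cost is one phrase in the next amendment, with no change to visits, data collection, sample size or analysis. Men who want the live vaccine would have it more than 30 days before treatment starts or defer it until 30 days after the last dose.
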